18 On C1D22, both pre-dose and post-dose plasma samples for PK of trametinib and dabrafenib will be collected. On C1D22, morning dose(s) should be withheld until after PK (pre-dose) sample has been drawn. On C1D22, post-dose PK samples for trametinib and/or dabrafenib should be drawn (1) at the same time as when the post-dose pembrolizumab PK sample is drawn (the end of infusion), and, (2) at approximately 4-6 hours post-dose. On C2D1, subjects should take their morning dose at home. A post-dose sample will be obtained during study visit. Thereafter, PK plasma samples will be collected at Day 1 of every alternate cycle (i.e., Day 1 of Cycle 3, Day 1 of Cycle 5, etc.) during study visit. If visit is in the morning, subjects will be asked to withhold their morning dose; if visit is in the afternoon, subjects will be asked to take their morning dose as usual. Procedures for collection of samples are described in the Procedures Manual.

19 The initial tumor imaging will be performed within 28 days prior to the date of allocation. Scans performed as part of routine clinical management are acceptable for use as the screening scan if they are of diagnostic quality and performed within 28 days prior to the first dose of trial treatment. CT scans are the required modality for measurable disease unless a subject has a clinical condition, e.g., severe contrast allergy. The same imaging technique has to be used for the subject throughout the study. The visit window for subsequent imaging is ± 7 days. If there is progressive disease, radiologic assessment/tumor imaging should be obtained at least four weeks from scan date for confirmation. CT timing should follow calendar days and should not be adjusted for delays in cycle starts. Response status will be assessed by the investigator. The process for collection of CT images is described in the Procedures Manual. Tumor imaging will be performed every 6 weeks (or whenever clinically indicated) starting at Week 13 while the subject remains on study therapy; after 18 months, tumor imaging will be performed every 12 weeks (or whenever clinically indicated) while the subject remains on study therapy. Per the modified RECIST 1.1 used in this protocol, if imaging shows progressive disease, the imaging assessment should be repeated at a minimum of 4 weeks later in order to confirm progressive disease as described in Section 4.2.3.1.

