8.2.3.1.1 Primary Endpoint

Progression-free Survival (PFS): is defined as the time from randomization in Part 3 (or the start of treatment in other Parts) to progressive disease (PD) or death, whichever occurs earlier, based upon RECIST 1.1 by the investigator review. Subjects without documented PD/death will be censored at the last disease assessment date.

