8.2.3.1.3 Exploratory Endpoints

Best Overall Response per RECIST 1.1 [Appendix 12.4]: the best response attained during the study with 4 categories based upon RECIST 1.1 by the investigator review: Complete Response (CR), Partial Response (PR), Stable Disease (SD), and Progressive Disease (PD). Categories of CR and PR need to be confirmed in this endpoint.

5-Category Best Overall Response (BOR-5) – an ordinal endpoint that represents the best response attained during the study with 5 categories: CR (confirmed), Very Good Partial Response (VGPR) defined as confirmed partial response with maximum percent reduction

from baseline in tumor line length >60%, Moderate Partial Response (MPR) defined as confirmed partial response with maximum percent reduction from baseline in tumor line length \leq 60%, SD, and PD. In this endpoint, CR, PR, SD and PD categories are based upon RECIST 1.1 by the investigator review and the RECIST 1.1 category of PR is split into two categories: VGPR and MPR.

5-Category Ordinal Response at a Timepoint – an ordinal endpoint that classifies the response at given timepoint into one of 5 categories: CR, VGPR defined as partial response with percent reduction from baseline in tumor line length >60%, MPR defined as partial response with percent reduction from baseline in tumor line length \leq 60%, SD, and PD. In this endpoint, CR, PR, SD and PD categories are based upon RECIST 1.1 by the investigator review. No confirmation will be required for complete or partial responses at a timepoint. Subjects who discontinued prior to timepoint will be assigned to one of these categories according to their reason for discontinuation. Subjects who discontinued for the following reasons will be included in the PD category: documented disease progression, unacceptable adverse event(s), intercurrent illness that prevents further administration of treatment, noncompliance with trial treatment or procedure requirements, investigator’s decision to withdraw the subject, subject withdraws consent. Subjects who discontinued due to pregnancy of the subject or for administrative reasons will be included in the SD category. Subjects who attained an investigator-determined confirmed complete response (CR) per RECIST 1.1 and stopped the trial treatment will be included in the CR category. The categories are assigned scores 1 to 5 for analysis: CR=1, VGPR=2, MPR=3, SD=4, PD=5.

Percentage of Subjects with CR based upon RECIST 1.1 by the investigator review

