Descriptive statistics according to the individual scoring will be provided for EuroQol (EQ-5D) and EORTC (QLQ-C30) by cycle and at the end of treatment for each treatment arm separately; additional modeling might be performed.

An exploratory analysis that relates PFS to BOR-5 will be conducted for each treatment group separately. Subjects will be classified according to their BOR; five PFS Kaplan-Meier curves will be plotted for each category of BOR and examined for presence of trend across the categories. In addition, potential of the 5-category Ordinal Response at a landmark to predict the PFS beyond the landmark will be explored in the following way. Subjects who had not experienced PD by Week 12 will be classified into 4 categories according to their 5-category Ordinal Response at Week 12. Four overlaid Kaplan-Meier curves for PFS beyond Week 12 will be plotted and examined for presence of trend across the categories. Similar

exploratory analysis will be performed for 5-category Ordinal Response at later weeks, although diminishing size of the data set will lead to higher variability of Kaplan-Meier curves.

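### PFS curves from randomization grouped by best overall response show a PD, SD, responder trend even when response is unrelated to progression, so only the landmark curves can link response to PFS (minor)

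*Combined protocol and SAP*

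**What the plan says.** All references are to the Combined protocol and SAP.

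- **Section 8.2.5.1** states: "An exploratory analysis that relates PFS to BOR-5 will be conducted for each treatment group separately". Subjects are classified by best response, and "five PFS Kaplan-Meier curves will be plotted for each category of BOR and examined for presence of trend across the categories".
- **Section 8.2.3.1.1:** PFS "is defined as the time from randomization in Part 3".
- **Section 8.2.3.1.3:** BOR-5 is "an ordinal endpoint that represents the best response attained during the study with 5 categories". Its CR and PR categories are confirmed responses, and the same holds for the four-category version: "Categories of CR and PR need to be confirmed in this endpoint".
- **Section 6.1.2** (imaging footnote): scans are done "every 6 weeks (or whenever clinically indicated) starting at Week 13 while the subject remains on study therapy", and "after 18 months, tumor imaging will be performed every 12 weeks".
- **Section 8.2.5.1, same paragraph,** adds a landmark analysis. Subjects without PD by Week 12 are placed in four categories by their Week 12 ordinal response. "Four overlaid Kaplan-Meier curves for PFS beyond Week 12 will be plotted and examined for presence of trend across the categories". Similar analyses follow at later weeks.

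For the five curves from randomization, the SAP gives no correction for the time needed to reach a category and does not label them descriptive.

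**The concern.** The clock starts at randomization, but the group label is set by what happens afterwards. A subject who progresses at the first scan can only be PD. A subject who would have responded but progresses before the confirming scan is moved down to SD or PD. A confirmed responder has, by construction, already survived progression-free past two scans. Part of the PFS difference between the curves is therefore put there by the classification.

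The SAP proposes to inspect these curves for a trend. A trend produced by the grouping itself says nothing about whether response carries information on later progression. What is at stake is an exploratory conclusion in the study report: a reader could take the ordered curves as support for the five-category response scale.

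**Working it through.** **Inputs from the documents.** About 120 subjects randomized 1:1, so about 60 per arm; control median PFS 10 months; hazard ratio 0.5, which under exponential PFS gives 20 months in the triplet arm; 0.5-year enrolment in a 2-year study, so 18 to 24 months of follow-up; dropout 5% a year (Section 8.2.7). Scheduled scans at Weeks 13, 19, 25 and so on, then every 12 weeks after 18 months (Section 6.1.2). Ten months is 43.5 weeks, in line with Section 8.2.5.1, which equates 44 weeks with 10.1 months.

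**The plan's own figure.** The documents give no number for these curves, so the figure to reproduce is the 74 events of Section 8.2.7. With exponential PFS, λ = ln 2/median, dropout hazard δ and uniform follow-up of 18 to 24 months:

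P(event) = λ/(λ+δ) × {1 − [e^(−18(λ+δ)) − e^(−24(λ+δ))]/[6(λ+δ)]}

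This is 0.739 at a 10-month median and 0.496 at 20 months. Expected events = 60 × (0.739 + 0.496) = 74.1, which agrees with the plan.

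**Null case by hand.** Assumptions not in the documents: 80% of subjects would respond if they stayed progression-free and 20% would not; any response is visible at the first scan; progression is exponential with a 43.5-week median whatever the response. Then S(13) = 2^(−13/43.5) = 0.813 and S(19) = 2^(−19/43.5) = 0.739.

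- **PD:** 1 − 0.813 = 18.7% of subjects, all with PFS recorded at Week 13.
- **Confirmed responders:** 0.80 × 0.739 = 59.1%, all progression-free at Week 19. Median 19 + 43.5 = 62.5 weeks, read at the Week 67 scan.
- **SD:** 0.20 × 0.813 = 16.3% who never respond, plus 0.80 × (0.813 − 0.739) = 5.9% who would have responded but progress before confirmation; 22.2% in all. The median solves (16.3/22.2) × 2^(−(t−13)/43.5) = 0.5, giving t of about 37 weeks.

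Medians of 13, 37 and 67 weeks arise with no association at all.

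**Null case by simulation.** Assumed latent depth: CR 10%, VGPR 35%, MPR 35%, none 20%. Three timing patterns: every depth reached at the first scan, moderate delay to deeper response, slow deepening. PD is read at the next scheduled scan, with no dropout. Each scenario has 1,000 arms of 60 subjects and uses a log-rank trend test at one-sided 0.025. The median of 16.2 months is 10 plus the 6.2-month gain stated in Section 8.2.7.

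At a 10-month median, the Kaplan-Meier medians in weeks for CR/VGPR/MPR/SD/PD were 67/67/67/37/13 (first scan), 85/67/67/37/13 (moderate) and 97/67/61/31/13 (slow).

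Percentage of arms with a false trend:

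| Median PFS, timing | Five categories | Without PD | Responders only | Landmarks, Weeks 13, 19, 37 |
|---|---|---|---|---|
| 10 mo, first scan | 98.9 | 20.0 | 2.0 | 2.0–2.7 |
| 10 mo, moderate | 99.2 | 33.2 | 3.5 | 2.0–3.0 |
| 10 mo, slow | 99.9 | 48.5 | 8.0 | 1.5–2.4 |
| 16.2 mo, first scan | 91.1 | 16.1 | 2.5 | 2.9–3.2 |
| 16.2 mo, moderate | 92.5 | 19.6 | 4.1 | 2.2–2.3 |
| 16.2 mo, slow | 95.8 | 34.8 | 6.7 | 1.7–2.9 |
| 20 mo, first scan | 84.3 | 13.1 | 2.7 | 2.7–3.7 |
| 20 mo, moderate | 86.4 | 20.0 | 3.7 | 2.3–3.4 |
| 20 mo, slow | 94.8 | 31.5 | 6.6 | 2.2–3.2 |

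The Monte Carlo standard error at 2.5% is √(0.025 × 0.975/1000) = 0.5 points, so the landmark rates sit around the nominal level. The simulated landmarks were placed on scan weeks; Week 13 is the nearest to the plan's Week 12.

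**The case against.** The case for leaving the plan alone has several parts.

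- **No decision depends on these curves.** They are exploratory, with no test, alpha or threshold. This stands, and it sets the weight of the point.
- **The unbiased analysis is already there.** The same paragraph plans landmark curves at Week 12 and later. It speaks of prediction only for those, and says of the BOR-5 curves only that they relate PFS to response. This also stands, and makes the remedy cheap. It does not rescue the five curves, which are still to be examined for trend.
- **The artefact does not run evenly through the scale.** This stands. It comes from PD versus SD versus responder. When every depth is reached at the first scan, CR, VGPR and MPR have the same median.

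A reader might infer more: that these curves are the plan's validation of the interim Go/No-Go endpoint. The documents do not support that. The interim endpoint is the Week 36 ordinal response by central review, with no confirmation required (Sections 8.2.3.1.2, 8.2.3.1.3 and 8.2.9.1). BOR-5 is a confirmed best response over the study by investigator review. The decision rule uses only the Week 36 ANOVA (Sections 8.2.9.2 and 8.2.9.2.1), and the rationale in Section 4.2.3.1.2 rests on depth and durability of shrinkage. Nor does the SAP rank the BOR-5 curves above the landmark curves; it merely lists them first.

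**Conclusion.** The point holds and is minor. A PD, SD, responder trend in the five curves from randomization is expected whether or not response is related to progression, so its presence is not evidence of a relation. The false-trend rate was 84% to 99.9% per 60-subject arm across all nine scenarios, against 1.5% to 3.7% for landmarks. It falls to 13% to 49% without the PD category and to 2% to 8% among confirmed responders, so the depth ordering is distorted only if deeper responses come late.

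The rates rest on an assumed response mix, assumed response timing, exponential PFS and scan-based progression. The plan calls for visual inspection, so they indicate how reliably a false trend would appear and are not the error rate of a planned test. The direction of the PD, SD, responder contrast follows from the definitions and does not depend on those assumptions. The consequence is confined to an exploratory conclusion; the primary PFS comparison and the interim rule are untouched.

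**What to change.** Do not examine the BOR-5 curves from randomization for trend. Either drop them, or show them labelled as descriptive, with a sentence saying that ordering by best response is expected from the definition. Base any statement that response relates to or predicts PFS solely on the landmark analyses already planned at Week 12 and later, or on response category as a time-dependent covariate in the stratified Cox model.

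No new data are needed. Subjects who progress before a landmark leave that plot, as the plan already provides. Section 8.2 lets changes to exploratory analyses be listed with an explanation in the study report, so no amendment is required. Section 5.2.5 records that the Part 3 final analysis has been done, so in practice the change concerns how these curves are reported.

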8.2.5.2 Pharmacokinetic Analysis

Serum concentrations of pembrolizumab will be summarized by planned visit and time and PK data will be compared to the existing population PK model. Graphical, non-compartmental and potentially exploratory compartmental analyses will be used for the analysis of the PK data.

Plasma concentrations of dabrafenib, hydroxy-dabrafenib, desmethyl-dabrafenib, and trametinib will be summarized by planned visit and time. PK parameters such as oral clearance (CL/F), volume of distribution (Vc/F) and other measures of exposure (average concentration [C_{avg}], and/or minimum concentration [C_{min}]) will be derived using previously validated models and summarized.

8.2.5.3 Biomarker Analysis

In Parts 1, 2, 4, and 5, the key biomarker will be the PD-L1 expression measured using 0-5 Allred Proportion Scores (APS) for PD-L1 staining in melanoma using the Dako assay. The mean change from baseline to Day 10-14 after administration of oral dabrafenib and/or trametinib in combination with intravenously administered pembrolizumab in PD-L1 expression will be estimated and the 95% CI for the change will be provided.

8.2.5.4 Statistical Methods for Safety Analyses

Safety and tolerability will be assessed by clinical review of all relevant parameters including AEs, SAEs, laboratory tests, vital signs, ECG measurements and physical examinations.

In Parts 1, 2, 4, and 5, DLTs will be listed. Adverse experiences will be summarized as counts and frequencies for each dose level in Parts 1, 2, 4, and 5 of the study. Laboratory assessments, vital signs, and other safety endpoints will be summarized as appropriate.

AEs of potentially immunologic etiology (AEs of special interest, AEOSI) will be identified using a pre-specified list of terms.

Part 3. The analysis of safety results in Part 3 will follow a tiered approach (Table 42). The tiers differ with respect to the analyses that will be performed. There are no Tier 1 events in this study; safety parameters will be considered Tier 2 or Tier 3. Tier 2 parameters will be assessed via point estimates with 95% confidence intervals provided for between-group comparisons; only point estimates by treatment group are provided for Tier 3 safety parameters.

Adverse experiences (specific terms as well as system organ class terms) and predefined limits of change in laboratory, vital signs, and ECG parameters will be classified as belonging to "Tier 2" or "Tier 3," based on the number of events observed. Membership in

Tier 2 requires that at least 4 subjects in any treatment group exhibit the event; all other adverse experiences and predefined limits of change will belong to Tier 3.

The threshold of at least 4 events was chosen because the 95% confidence interval for the between-group difference in percent incidence will always include zero when treatment groups of equal size each have less than 4 events and thus would add little to the interpretation of potentially meaningful differences. Because many 95% confidence intervals may be provided without adjustment for multiplicity, the confidence intervals should be regarded as a helpful descriptive measure to be used in review, not a formal method for assessing the statistical significance of the between-group differences in adverse experiences and predefined limits of change.

Continuous measures such as changes from baseline in laboratory, vital signs, and ECG parameters that are not pre-specified as Tier-1 endpoints will be considered Tier 3 safety parameters. Summary statistics for baseline, on-treatment, and change from baseline values will be provided by treatment group in table format.

In addition, the broad clinical and laboratory AE categories consisting of the percentage of subjects with any AE, a drug related AE, a serious AE, an AE which is both drug-related and serious, and who discontinued due to an AE will be considered Tier 2 endpoints.

AEs of potentially immunologic etiology (AEs of special interest [AEOSI]) will be identified using a pre-specified list of terms and summarized.

Table 42 Analysis Strategy for Safety Parameters

Safety Tier	Safety Endpoint [†]	p-Value	95% CI for Treatment Comparison	Descriptive Statistics
Tier 2	Any AE		X	X
	Any Serious AE		X	X
	Any Grade 3-5 AE		X	X
	Onset and Duration of First Grade 3-5 AE		X	X
	Any Drug-Related AE		X	X
	Any Serious and Drug-Related AE		X	X
	Any Grade3-5 and Drug-Related AE		X	X
	Dose Modification due to AE		X	X
	Discontinuation due to AE		X	X
	Death		X	X
	Specific AEs, SOCs, or PDLCs [‡] (incidence \geq 4 subjects in at least one of the treatment groups)		X	X
Tier 3	Specific AEs, SOCs or PDLCs [‡] (incidence <4 subjects in all of the treatment groups), AEO SI			X
	Change from Baseline Results (Labs, ECGs, Vital Signs)			X

[†] Adverse Experience references refer to both Clinical and Laboratory AEs.
[‡] Includes only those endpoints not pre-specified as Tier-2 endpoints.
 Note: SOC=System Organ Class; PDLC=Pre-Defined Limit of Change; X = results will be provided.

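### Table 42 puts the pooled AEOSI grouping in Tier 3 at any count, so Part 3 plans no between-arm confidence interval for immune-related AEs taken together

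*Combined protocol and SAP*

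**What the plan says.** Section 8.2.5.4 sets up a tiered safety analysis for Part 3, with no Tier 1 events. Tier 2 parameters have "95% confidence intervals provided for between-group comparisons"; by contrast, "only point estimates by treatment group are provided for Tier 3 safety parameters".

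The sorting rule covers "Adverse experiences (specific terms as well as system organ class terms) and predefined limits of change in laboratory, vital signs, and ECG parameters". Membership of "Tier 2 requires that at least 4 subjects in any treatment group exhibit the event", and everything else in that scope falls to Tier 3. The justification is that the interval for the difference "will always include zero when treatment groups of equal size each have less than 4 events".

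A set of broad AE categories (any AE, drug-related, serious, leading to discontinuation and similar) is Tier 2 regardless of count. AEOSI is not among them, in the text or in Table 42.

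On AEOSI the text says only: "AEs of potentially immunologic etiology (AEs of special interest [AEOSI]) will be identified using a pre-specified list of terms and summarized". It names no tier. Table 42 does: the Tier 3 row ends "incidence <4 subjects in all of the treatment groups), AEO SI", with only the descriptive-statistics column marked. (The split in the last word comes from text extraction.) The Tier 2 row for specific AEs, SOCs and predefined limits of change applies at "4 subjects in at least one of the treatment groups" or more and does not exclude immune-related terms.

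**The concern.** Every other entry in Table 42 that rests on event counts is placed by incidence or is a broad category fixed in Tier 2. The AEOSI grouping is placed in Tier 3 by its label alone, and no reason is given.

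The grouping matters in this trial. By design the Part 3 arms differ only in pembrolizumab versus saline (Section 1.0), and Section 5.6.1.1.3 ties immune-related AEs to pembrolizumab's mechanism. Section 5.6.1.1 also lists toxicities common to all three drugs, among them diarrhea, pneumonitis, pyrexia and skin and ocular events. The control arm may therefore contribute AEOSI counts too. The informative quantity is then the difference between arms with its uncertainty, and the plan does not provide that uncertainty for the pooled grouping.

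**Working it through.** **Inputs.** 60 subjects per arm (Section 1.0); Tier 2 cut-off of 4 subjects in any arm (Section 8.2.5.4). Two assumptions are needed. The documents give no AEOSI rate, so a range is used. They name no interval method for safety differences, so the Miettinen–Nurminen score interval is used, as named for ORR in Table 40, with the Wald interval as a check.

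**Step 1: the plan's own rationale.** Wald interval: d ± 1.96 × √[p1(1−p1)/60 + p2(1−p2)/60].

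- 3 vs 0: d = 0.05; SE = √(0.05 × 0.95/60) = 0.0281; 95% CI −0.5 to 10.5 points. Miettinen–Nurminen: −1.2 to 13.8.
- 4 vs 0: d = 0.0667; SE = √(0.0667 × 0.9333/60) = 0.0322; 95% CI 0.35 to 13.0 points. Miettinen–Nurminen: 0.4 to 16.0.

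With Miettinen–Nurminen at 60 per arm, every pair of counts below 4 gives an interval that includes zero. The 3 vs 0 and 4 vs 0 results also hold at 40, 55 and 65 per arm. The stated rationale reproduces, and it is silent on counts of 4 or more.

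**Step 2: would a pooled AEOSI count reach 4?** P(X ≥ 4) = 1 − Σ(k=0..3) C(60,k) p^k (1−p)^(60−k). At p = 0.10 the terms for k = 0 to 3 are 0.0018, 0.0120, 0.0393 and 0.0844, which sum to 0.1374 on unrounded values, so P = 0.86.

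| Assumed true rate in an arm | P(at least 4 of 60) |
|---|---|
| 5% | 0.35 |
| 10% | 0.86 |
| 15% | 0.985 |
| 20% | 0.999 |

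**Step 3: does the route through individual terms close the gap?** Not necessarily. Table 10 spreads immune-related AEs over lung, gut, liver, endocrine organs, kidney and heart. Suppose five terms in five different SOCs each occur at 3 vs 0, in different subjects, with no other events taking those SOCs to 4. Each term is 5 points (−0.5 to 10.5, Wald) and stays in Tier 3. Pooled, the count is 15 vs 0: d = 0.25; SE = √(0.25 × 0.75/60) = 0.0559; 95% CI 14.0 to 36.0 points. The plan would report none of these intervals.

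**Step 4: what a pooled interval would show.** Counts are illustrative; Miettinen–Nurminen, 60 per arm.

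| Counts | Difference (points) | 95% CI |
|---|---|---|
| 6 vs 3 | 5 | −5.2 to 15.9 |
| 12 vs 3 | 15 | 3.4 to 27.6 |
| 18 vs 6 | 20 | 5.9 to 34.1 |

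**The case against.** The strongest reply has four parts.

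- **No contradiction.** A reader might infer that Table 42 breaks the 4-subject rule. The documents do not support that. The rule names specific terms, SOC terms and predefined limits of change; a pooled grouping is none of these. It also words 4 subjects as a requirement for Tier 2, without promising an interval to every category that reaches it. Text and table would conflict only if the table entry were read as taking individual AEOSI terms out of the Tier 2 row, and nothing says so. This stands: the placement is an unexplained exception.
- **Immune-related events are not left without intervals.** A reader might infer that they get none. In fact, a listed term or its SOC with at least 4 subjects in an arm falls in the Tier 2 row, and intervals are planned for broad categories such as any Grade 3-5 AE, any serious AE and discontinuation due to an AE. This stands too. Step 3 shows why it does not fully replace a pooled interval, and the broad categories mix immune-related with other events.
- **Little depends on it.** Section 8.2.5.4 treats these intervals as descriptive and unadjusted for multiplicity, and a reader could compute one from the reported counts. True, but the same section considers such intervals helpful enough to give them to any unrelated term at 4 subjects.
- **It is late.** Section 5.2.5 reports the Part 3 final analysis as done, so editing Table 42 now is not pre-specification. This stands and shapes the fix.

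**Conclusion.** The point holds for the pooled AEOSI grouping only. Part 3 plans no between-arm 95% CI for it at any count, and the one stated reason for withholding intervals does not reach counts of 4 or more. Whether the pooled count would reach 4 depends on an incidence that the documents do not give: it is likely at a true rate of 10% or above in an arm of 60 (0.86 or higher) and less likely than not at 5% (0.35). The example of 15 versus 0 shows what is possible and is not a forecast. The consequence is a gap in descriptive safety reporting on a contrast closely tied to adding pembrolizumab. The primary analysis, the decision rules and all error rates are unaffected.

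**What to change.** In Table 42 and the text of Section 8.2.5.4:

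1. Add any AEOSI and Grade 3-5 AEOSI as Tier 2 rows with a descriptive 95% CI for the treatment difference, treated like the existing broad AE categories.
2. State that individual AEOSI terms follow the same 4-subject rule as other AEs.
3. Delete the unconditional AEOSI entry from the Tier 3 row.

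Because the Part 3 final analysis has been done, present these intervals in the CSR as added later, with the reason and the interval method. The opening of Section 8.2 already provides for changes to non-confirmatory analyses to be listed there. The cost is a few intervals from events already identified through the pre-specified term list. No new data and no change to conduct are needed.
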